10.4 Vital Signs

Descriptive summaries (mean, SD, median, minimum, and maximum) of actual values and changes from each baseline at each assessment time point and last on-treatment assessment will be calculated for vital signs including weight, BMI, body temperature, pulse rate, systolic blood pressure and diastolic blood pressure. 95% confidence intervals will be presented for change from each baseline.

These summaries will be presented by treatment and assessment time for the Safety population. ET data will be analyzed with the closest visit that does not have a valid assessment value.

10.5 Visual Examination of Oral Cavity

A visual examination of the oral cavity will be assessed at Baseline and Week 12. A visual examination is to be done any time a participant spontaneously reports an oral adverse event (aside from AEs known to be sensory-only, such as numbness, tingling or bitter taste) to confirm presence or absence of any signs of irritation or other visible

abnormalities. A data listing of the visual examination results performed at each scheduled visit and at the time of an adverse event will be presented.

11. MEDICATIONS

11.1 Concomitant Medication

All medications will be coded using the World Health Organization Drug Dictionary (WHO-DD) Version September 2016. Prior and concomitant medications will be summarized by treatment group and by the number and percentage of participants taking each medication, classified by using WHO-DD Anatomical Therapeutic Chemical Level 3 and preferred term.

Prior medications are defined as medications or therapies initiated prior to the start of the study drug and terminating prior to the start of study drug in protocol P301. Hence, these medications or therapies will have end dates prior to the first dose date of study drug.

Concomitant medications are defined as any medications other than the study drug that a participant receives concurrently with the study drug. These medications will have end dates on or after the first dose date of the study drug until ten days after last dose date.

There should be no new prior medications recorded in protocol P303 as these should be captured entirely in P301. Concomitant medications will be summarized by treatment group. All medications will be presented in a listing.

Please refer to [Section 7.3](#) for the conventions used to impute partial start dates and end dates of concomitant medications.

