7.3.1 Adverse Event and Prior/Concomitant Medication handling conventions

To handle missing or partial AE and prior/concomitant medication dates, the following rules will be applied.

For partial start dates:

1. If the year is unknown, then do not impute the date but assign a missing value.
2. If the month is unknown, then:
 - a. If the year matches the year of the first dose date, then impute the month and day of the first dose date.
 - b. Otherwise, assign “January.”
3. If the day is unknown, then:
 - a. If the month and year match the month and year of the first dose date, then impute the day of the first dose date.
 - b. Otherwise, assign “01.”

For partial end dates:

1. If the year is unknown, then do not impute the date but assign a missing value.
2. If the month is unknown, then assign “December.”
3. If the day is unknown, then assign the last day of the month.

After implementing the rules above, to determine whether medications with missing start or stop dates are prior or concomitant medications, the following strategy will be used:

1. If the start date and stop date are both missing, then the most conservative approach is taken and the medication is considered to be a concomitant medication.
2. If the start date is missing but the stop date is not missing and is after the day of first study dose administration, then the most conservative approach is taken and the medication is considered to be concomitant.
3. If the start date is missing but the stop date is not missing and is on or before the day of first study dose and after the date of signed informed consent, then the medication is considered to be a prior medication.
4. If the start date is not missing but the stop date is missing, then the most conservative approach is taken and medication is considered to be concomitant.

The missing severity of an AE will be imputed to “severe”; the missing relationship to study drug of an AE will be imputed to “related”.

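### The date rule for concomitant medications in SAP 11.1 tests only the end date and caps it at ten days after last dose, so some drugs taken during treatment fall out of the concomitant table

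*SAP*

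**What the plan says.** SAP 11.1 gives a concept and then a date rule. The concept is "any medications other than the study drug that a participant receives concurrently with the study drug". The date rule is "These medications will have end dates on or after the first dose date of the study drug until ten days after last dose date". Prior medications are those "terminating prior to the start of study drug in protocol P301". The next sentence says that "these medications or therapies will have end dates prior to the first dose date of study drug" and does not name the study. The section adds: "There should be no new prior medications recorded in protocol P303 as these should be captured entirely in P301". It also promises a listing of all medications.

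SAP 7.3.1 first completes partial dates. For an end date with an unknown month it assigns December, and for an unknown day: "If the day is unknown, then assign the last day of the month". It then applies four rules to records that still lack a date:

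- Rule 1: "If the start date and stop date are both missing, then the most conservative approach is taken", and the drug is concomitant.
- Rule 2: start missing, stop after the first dose day: concomitant, with no upper limit.
- Rule 3: start missing and a stop that "is on or before the day of first study dose and after the date of signed informed consent": prior.
- Rule 4: start known, stop missing: concomitant.

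**The concern.** The concept and the date rule in SAP 11.1 give different answers for the same drug, and a programmer would normally code the date rule. That rule has no condition on the start date and sets an upper limit on the end date. Whether a drug was taken during treatment depends on overlap: it started by the last dose and had not ended before the first. An end date well after the last dose does not make a drug less concurrent.

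Safety is the primary objective, and Protocol 8.5 relaxes the lead-in restrictions so that antidepressants, benzodiazepines and opioids may be used, with a caution about serotonin syndrome. The concomitant medication table is the planned summary of those exposures. A rule that leaves out some drugs taken on treatment and lets in some that were not makes that table wrong for the records concerned.

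**Working it through.** The plan gives no figure to reproduce, so the check runs test records through both sections and then counts calendar dates.

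**Test records.** Assumed dates: first P301 dose 2017-07-01, first P303 dose 2017-09-23, last P303 dose 2017-12-15 (first dose + 83 days). The cap is 2017-12-15 + 10 days = 2017-12-25. In the SAP 11.1 column, first dose means first P303 dose for concomitant and first P301 dose for prior.

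| Record | SAP 11.1 date rule | SAP 7.3.1 |
|---|---|---|
| Start known, end = last dose + 10 | concomitant | no rule applies |
| Start known, end = last dose + 11 | neither class | no rule applies |
| Start known, end recorded only as December 2017, imputed to 2017-12-31 | neither class | no rule applies, as the stop date is no longer missing |
| Start missing, end = last dose + 11 | neither class | concomitant (rule 2) |
| Start known, no stop date | cannot be evaluated | concomitant (rule 4) |
| Both dates missing | cannot be evaluated | concomitant (rule 1) |
| Start missing, end = first P303 dose day | concomitant | prior (rule 3) if consent was on an earlier day; no rule if consent was the same day |
| Start known, end during P301 treatment | neither class | no rule applies |

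A drug started one day after the last dose and stopped five days after it has an end date inside the window. The date rule admits it although it was never taken together with study drug.

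**Day of the stop unknown, stop in the month of last dose.** The imputed end is day D of a D-day month. It passes the cap when D − (day of last dose) > 10, that is, for last doses on days 1 to D − 11. The share is (D − 11)/D:

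- 28-day month: 17/28 = 60.7%
- 30-day month: 19/30 = 63.3%
- 31-day month: 20/31 = 64.5%

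Assume last-dose dates from 2017-09-01 to 2018-12-10, in line with the protocol synopsis (first enrolment June 2017, last completion December 2018). The 15 full months have 456 days, of which 456 − 15 × 11 = 291 pass. All of 1 to 10 December 2018 pass, adding 10. Total: 301 of 466 = 64.6%. Extending the range to 31 December 2018 gives 487 − 16 × 11 = 311 of 487 = 63.9%.

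**Month of the stop unknown, stop in the year of last dose.** The imputed end is 31 December. It passes the cap for any last dose before 21 December: 365 − 11 = 354 of 365 dates (97.0%).

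Both figures are shares of calendar dates. They apply only to records that have such a partial end date.

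**The case against.** The best defence is that the concept sentence governs and the date sentence merely illustrates it. On that reading every drug taken during treatment qualifies and a drug started after the last dose does not. This shows what was intended, but the date sentence is the only operational rule for a drug with both dates known, and it contradicts the concept.

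The second defence is that the omission will be uncommon, and this largely stands. Medications are last assessed at Visit 5 or Early Termination (Protocol 9.4, 9.5 and Appendix 1), and no post-treatment visit is scheduled. SAP 7.1 follows early terminators further only for an ongoing adverse event or other condition. A drug still in use at the final visit would normally have no stop date, and rule 4 keeps it. Protocol 8.5 also requires treatment dates to be recorded, which limits partial dates. The exposed cases are mainly patients who stopped study drug more than ten days before their last visit, which Protocol 9.5 foresees, and patients followed for an event.

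A reader might infer more than the documents support:

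- **That on-treatment drugs are called prior.** The cap never makes a drug prior, and end-date imputation only moves dates later. The label needs rule 3: a missing start date and a stop after consent but no later than the first dose day. Consent is taken at Visit 1 (Protocol 9.1.2) and dosing starts that evening (Protocol 9.1.4), so on the planned schedule no stop date satisfies rule 3. It applies only if dosing is delayed, or if consent is read as P301 consent. Even then a stop on a day with bedtime dosing is a boundary case.
- **That exposures are lost or adverse event rates distorted.** All medications are listed. The adverse event summaries in SAP 10.1 and the efficacy analyses in SAP 9 do not use the class.
- **That about 65% of patients or records are affected.** The documents give no count of partial dates.

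**Conclusion.** The date rule in SAP 11.1 is wrong as written. It omits from the concomitant table some drugs taken during treatment: those with a recorded end date more than ten days after last dose, and those with a partial end date imputed past that cap. It would admit a drug taken only after the last dose, and it disagrees with rule 2 of SAP 7.3.1. The disagreement with rule 3 over a stop on the first dose day is real in the text but nearly empty on the planned schedule.

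The consequence is small and confined to a descriptive table. The number of affected records is unknown and likely small. The calendar shares rest on an assumed range of last-dose dates, but they move little with it: 60.7% to 64.5% by month length. The conclusion assumes that the date sentence is programmed literally.

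**What to change.** Replace the date sentence in SAP 11.1 with an overlap rule: start date on or before the last P303 dose (or missing), and end date on or after the first P303 dose (or missing or ongoing), with no upper limit on the end date. If the ten days are meant as a post-dose window, apply them to the start date.

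Keep prior tied to the first P301 dose. Moving it to the first P303 dose would label drugs stopped during P301 treatment as prior, against the definition in SAP 11.1 and its expectation of no new prior medications in P303. State that drugs stopped between the two first doses belong to neither class and appear in the listing only. Name P301 or P303 at each mention of first dose.

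Align SAP 7.3.1 with this. Rule 2 should take a stop on or after the first P303 dose, and rule 3 a stop before the first P301 dose, so that a stop on the first P303 dose day is concomitant in both sections. Rule 4 needs the same start-date condition as the overlap rule.

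The cost is a few SAP sentences and one derivation before database lock. No new data are needed.

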11.2 Exposure and Compliance

The treatment duration will be calculated as (number of days=last dose date - first dose date+1) and summarized. Participants that are lost to follow up or have a missing last dose date will be assigned a last dose date of the day before the last attended clinic visit for analysis purposes.

All pill count shortage (negative pill count) of greater than 4 doses (8 tablets) per 4-week assessment period and/or any between-visit compliance <70% will be considered protocol deviations, and the reason for the pill count discrepancy will be discussed with the participant and documented in the CRF to ensure that any cases of potential abuse or misuse are identified. Participants with more than one significant incidence of negative pill count discrepancy during the double-blind phase of the study will be closely monitored by the investigator.

Exposure will be measured using the last date of treatment and first date of treatment. Total exposure will be defined as the last date of treatment minus the first date of treatment plus one. The number of participants with total exposure by visit weeks (≤ 4 weeks (study day 0 to 28), 4 to ≤ 8 (study day 29 to 56), 8 to ≤ 12 (study day 57 to 84) and > 12 weeks (study day ≥ 85)) will be presented. Additionally, exposure days, defined as the total number of tablets taken divided by 2 (and rounded up to the nearest whole number), will be summarized.

Compliance will similarly be summarized across all study visits for each treatment arm. Study drug compliance as a percentage will be defined as the number of pills taken by the participant divided by the total number of pills that the participant was assigned to take multiplied by 100.

For calculating the compliance and exposure days, the following convention will be applied: for periods where drug is issued, but the participant does not return any bottles or tablets, or the participant misses the visit entirely, that period will not contribute to the compliance or exposure calculation unless the bottles are returned at a later visit.

Compliance will be summarized with descriptive statistics by treatment arm. The number and percentages of participants within certain categories of compliance e.g. < 50%, 50% to < 70%, 70% to <= 100%, greater than 100% will be presented. Compliance between 70% to 114% will not be considered a protocol deviation. Tablet counts, calculation of compliance overall and by visit, and participant-reported reasons for all tablet discrepancies at all visits will be presented in a listing.

In addition, participants with significant over-usage or otherwise unaccounted-for missing tablets resulting in >114% compliance for any visit (e.g., failure to return >8 tablets per 4 week interval) will be summarized by visit and overall. These listings will include both the participant-reported reason for the discrepancy plus the investigator's assessment of potential abuse, misuse or diversion. Tables will be created for higher level abuse-related MedDRA terms. Clinically significant drug accountability discrepancies associated with missing medication, loss of drug, or cases in which the PI confirms concern over drug abuse, misuse or diversion, will be examined and discussed in the CSR.

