6. INVESTIGATIONAL PLAN

6.1. Overall Study Design

This is a 12-week, multicenter, open-label extension study designed to accumulate additional safety exposure and efficacy data with daily bedtime dosing of TNX-102 SL 5.6 mg (2 x 2.8mg tablets) in patients with PTSD. This study will be conducted at approximately 35 sites in the United States (US).

Patients who have completed participation in a Phase 3, randomized, double-blind, placebo-controlled study comparing TNX-102 SL 5.6 mg versus placebo for the treatment of PTSD will be eligible. This extension study consists of 5 visits, including the Screening/Baseline visit (which is anticipated to be the same as the primary outcome visit in the double-blind lead-in study), a telephonic visit at week 2, and in-clinic visits after 4, 8 and 12 weeks of treatment (Visits 3-5). The total treatment duration of this study will be 12 weeks. Therefore, the maximum total duration of continuous treatment with TNX-102 SL could be approximately 24 weeks for those patients assigned to active study drug in the lead-in study.

Patient data collected at the Week 12 visit in the lead-in study will be used as one of the defined baselines for this study. There is no need to repeat assessments at Visit 1 for this study, if they were collected in the lead-in study and patients enroll and initiate study treatment within fourteen days of completing the lead-in study.

After the patient has completed his/her participation in the lead-in study and has consented to participate in this open-label extension study, patients will be dispensed a 4-week supply of open-label TNX-102 SL tablets and will be instructed to take the study drug sublingually daily at bedtime, starting on the evening of Visit 1. A phone visit will be completed after 2 weeks of treatment and patients will return to the study center for safety and efficacy assessments at Weeks 4, 8, and 12 (or early termination). At the Weeks 4 and 8 visits patients will return their TNX-102 SL medication and will receive another 4-week supply. Patients will be allowed to take medications deemed appropriate by their health care providers to manage their PTSD and other conditions, including currently approved PTSD therapies. See [Section 8.5](#) for a discussion of allowed concomitant treatments.

The study timeline and events schedule is provided in [Appendix 1](#).

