9.2. Visit 2 (Telephone Visit: Week 2)

Visit 2 will be done as a telephone call to the patient and should be conducted after 2 weeks of treatment, on Day 14 ± 3 days.

The following steps should be completed:

- Assess changes in concomitant medications
- Assess study drug compliance based on patient verbal report
- Assess occurrence of adverse events, including any oral adverse events and whether an unscheduled visit is indicated for an examination of the oral cavity
- Review patient instructions regarding drug dosing

- Administer the 'Since Last Visit' C-SSRS telephonically

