6. ANALYSIS POPULATIONS

The following analysis populations are planned for this study:

- **Safety Population (SAFETY):** All participants who receive at least 1 dose of study drug. Participants who are issued study drug, but return 100% of it (i.e., none consumed) will be excluded from the safety population; likewise, participants that have no follow up following receipt of study drug to indicate they took drug are excluded. All safety analyses and demographic/baseline characterization will be performed using this population.

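### SAP 11.2 can leave never-returned study drug out of the >114% unaccounted-for-tablet summary, and can impute 0 days of treatment to a treated patient last reached by the Week 2 call

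*SAP*

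**What the plan says.** All of the analysis rules at issue are in SAP 11.2. Compliance is tablets taken divided by tablets assigned, times 100. For a period in which drug is issued but no bottles or tablets come back, or the visit is missed, "that period will not contribute to the compliance or exposure calculation unless the bottles are returned at a later visit". A separate summary and listing, carrying the patient's reason and the investigator's view on abuse, misuse or diversion, covers significant over-usage or "unaccounted-for missing tablets resulting in >114% compliance for any visit (e.g., failure to return >8 tablets per 4 week interval").

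Treatment duration is last dose date minus first dose date plus one. A patient who is lost to follow-up, or whose last dose date is missing, "will be assigned a last dose date of the day before the last attended clinic visit for analysis purposes". A second measure is "exposure days, defined as the total number of tablets taken divided by 2", rounded up.

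Protocol 8.1 dispenses 80 tablets (two bottles of 40) at Visits 1, 3 and 4. Dosing is two tablets a night, starting on the evening of Visit 1 (Protocol 8.2 and 9.1.4). Protocol 6.1 describes "a telephonic visit at week 2, and in-clinic visits after 4, 8 and 12 weeks of treatment (Visits 3-5"). Protocol 9.2 places the Week 2 call at Day 14 ± 3 and includes this task: "Assess study drug compliance based on patient verbal report". The Appendix 1 schedule, however, puts Visit 2 under the column heading Clinic Visits. SAP 6 says that "participants that have no follow up following receipt of study drug to indicate they took drug are excluded" from the Safety Population.

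**The concern.** Safety is the primary objective, and SAP 11.2 says pill-count discrepancies are documented so that potential abuse or misuse is identified. The summary aimed at unaccounted-for tablets is triggered by a percentage, and the non-return convention removes that percentage in the most complete case of unaccounted-for tablets. Partial non-return is therefore displayed where total non-return may not be.

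The duration rule has a similar gap. The Week 2 call can establish that a patient took drug, which keeps that patient in the Safety Population, but the imputation looks only at clinic visits. If Visit 1 was the only one, the imputed last dose falls on the day before dosing began. What is at stake is the accuracy of the accountability display and of the continuous duration summary, not any inference.

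**Working it through.** **The plan's own threshold.** Assigned tablets over 28 days: 2 × 28 = 56. Failing to return 8 more than assigned gives (56 + 8)/56 = 64/56 = 114.29%, so the 114% figure reproduces after rounding.

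**Never-returned tablets at an attended visit.** Dispensed = 80; assigned = 2d for d days since dispensing; apparent compliance = 80/(2d). It is apparent only, since it treats all 80 as taken and true consumption is unknown.

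| d (days) | Assigned | 80/(2d) | Beyond assigned |
|---|---|---|---|
| 21 | 42 | 190.5% | 38 |
| 28 | 56 | 142.9% | 24 |
| 34 | 68 | 117.6% | 12 |
| 35 | 70 | 114.29% | 10 |
| 36 | 72 | 111.1% | 8 |
| 42 | 84 | 95.2% | −4 |

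The first period runs 28 ± 7 = 21 to 35 days, so every in-window Visit 3 exceeds the written 114%. Day 35 exceeds it only because 8/7 was rounded down: 10 tablets equals the 8-tablet limit prorated to 35 days (8 × 35/28 = 10). Later periods can run from (56 − 7) − (28 + 7) = 14 days to (56 + 7) − (28 − 7) = 42 days, and from Day 36 the trigger is not met.

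At Day 28, then, two empty bottles give 142.9% and enter the summary. Attending with nothing, and returning nothing later, gives no compliance value and so nothing to compare with 114%.

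**Missed visit.** If Visit 3 is missed, the 80 tablets span Visit 1 to Visit 4, which is 56 ± 7 = 49 to 63 days. Apparent compliance is 80/98 = 81.6% to 80/126 = 63.5%, never above 114%. If the patient never comes back, the interval has no end and no percentage exists.

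**Duration.** Count the first dose as protocol Day 0.
- Call not a clinic visit: last clinic visit is Day 0, imputed last dose is Day −1, and duration is −1 − 0 + 1 = 0 days.
- Call counts: calls on Days 11, 14 and 17 give last doses on Days 10, 13 and 16, and durations of 11, 14 and 17 days.

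All of these fall in the SAP's ≤4-week category. If the same patient never returns the first bottles, that period also drops out of tablet-based exposure days, and neither measure records any dosing.

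**The case against.** The strongest reply on tablets is that the non-return convention governs only the compliance and exposure-day calculations. The summary speaks of unaccounted-for tablets and offers failure to return more than 8 as its example, so a programmer could include total non-return on that wording. This is a fair reading. But the example illustrates a criterion expressed as a compliance value, and the convention removes that value. One section supports two outputs, and that needs settling.

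It is also fair that much is caught elsewhere. A reader might infer that never-returned drug disappears from reporting altogether; the documents do not support that. A shortage of more than 8 tablets per 4 weeks is a protocol deviation whose reason goes in the CRF (SAP 11.2), and deviations are tabulated (SAP 8.2). Tablet counts and reasons are listed. Clinically significant discrepancies involving missing drug, and "cases in which the PI confirms concern over drug abuse, misuse or diversion, will be examined and discussed in the CSR", with no 114% condition. These safeguards are partial: a reason has to be obtained from a patient who may not come back. Nor should a reader take 142.9% as evidence of over-use. It is what the formula would show, not what was swallowed, and it applies only to attended visits up to 35 days after dispensing.

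On duration, the reply is that several conditions must coincide: lost to follow-up or no last dose date, no early-termination or unscheduled clinic visit, a call that shows dosing, and a call that is not a clinic visit. All of that stands. The protocol and SAP text favour treating the call as separate from clinic visits; the contrary reading rests on one heading in a schedule table.

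A reader might go further and conclude that the 0-day result drops a definable set of concomitant medications, or that the lost-to-follow-up rule is wrong even where a last dose date was recorded. Neither is supported. SAP 11.1 first defines concomitant by concurrent use and lists all medications, and SAP 7.3.1 imputes partial stop dates late and treats missing ones as concomitant. Nothing in the documents shows the lost-to-follow-up rule to be wrong in general.

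**Conclusion.** The point holds as a minor one. Read literally, SAP 11.2 keeps a never-returned period out of the >114% summary and its listing with the investigator's assessment, although that summary's example describes such a case. It also yields 0 days of treatment for a treated patient whose only post-baseline contact was the Week 2 call, against 11 to 17 days if the call counts.

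The tablet contrast assumes an attended visit no more than 35 days after dispensing and bottles that never come back. The duration result assumes a first dose on the evening of Visit 1, as instructed, and that the call is not a clinic visit. The number of patients in either situation is unknown. The effect is descriptive: the ≤4-week count is unchanged, the SAP plans no exposure-adjusted event rate, and no test is altered.

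**What to change.** In SAP 11.2:

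- Keep never-returned periods out of the compliance percentage, but count and list them beside the >114% summary as a separate category, *not returned, consumption unknown*. Give the reason where recorded, and keep the category apart from confirmed over-use.
- State whether Visit 2 counts as an attended visit for the last-dose imputation. Whichever is chosen, do not let the imputed last dose date fall before the first dose date, so that every Safety Population patient has at least 1 day.

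The cost is SAP wording and minor programming. The floor needs no new data. Counting the call needs its date in the database; the protocol requires a verbal compliance check there, but does not say that a dosing date is recorded. The downside is that forgotten bottles and ordinary dropouts will appear in the new category, often without a reason, which is why it must not be merged with over-use.
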